### 10.3.2. Definition of SAE

If an event is not an AE per definition above, then it cannot be an SAE even if serious conditions are met (eg, hospitalization for signs/symptoms of the disease under study, death due to progression of disease).

An SAE is defined as any untoward medical occurrence that, at any dose:
a. Results in death
b. Is life-threatening  The term “life-threatening” in the definition of “serious” refers to an event in which the participant was at risk of death at the time of the event. It does not refer to an event that hypothetically might have caused death if it were more severe.

**c. Requires inpatient hospitalization or prolongation of existing hospitalization**

In general, hospitalization signifies that the participant has been detained (usually involving at least an overnight stay) at the hospital or emergency ward for observation and/or treatment that would not have been appropriate in the physician's office or outpatient setting. Complications that occur during hospitalization are AEs. If a complication prolongs hospitalization or fulfills any other serious criteria, the event is serious. When in doubt as to whether "hospitalization" occurred or was necessary, the AE should be considered serious.

Hospitalization for elective treatment of a preexisting condition that did not worsen from baseline is not considered an AE.

**d. Results in persistent disability/incapacity**

- The term disability means a substantial disruption of a person's ability to conduct normal life functions.
- This definition is not intended to include experiences of relatively minor medical significance such as uncomplicated headache, nausea, vomiting, diarrhea, influenza, and accidental trauma (eg, sprained ankle) which may interfere with or prevent everyday life functions but do not constitute a substantial disruption.

**e. Is a congenital anomaly/birth defect**

**f. Other situations:**

- Medical or scientific judgment should be exercised in deciding whether SAE reporting is appropriate in other situations such as important medical events that may not be immediately life-threatening or result in death or hospitalization but may jeopardize the participant or may require medical or surgical intervention to prevent one of the other outcomes listed in the above definition. These events should usually be considered serious.
- Examples of such events include invasive or malignant cancers, intensive treatment in an emergency room or at home for allergic bronchospasm, blood dyscrasias or convulsions that do not result in hospitalization, or development of drug dependency or drug abuse.
- Suspected transmission via a Pfizer product of an infectious agent, pathogenic or non-pathogenic, is considered serious. The event may be suspected from clinical symptoms or laboratory findings indicating an infection in a patient exposed to a Pfizer product. The terms "suspected transmission" and "transmission" are considered synonymous. These cases are considered unexpected and handled as

serious expedited cases by pharmacovigilance personnel. Such cases are also considered for reporting as product defects, if appropriate.

### 10.3.3. Recording/Reporting and Follow-up of AEs and/or SAEs

#### AE and SAE Recording/Reporting

The table below summarizes the requirements for recording adverse events on the CRF and for reporting serious adverse events on the CT SAE Report Form to Pfizer Safety. These requirements are delineated for 3 types of events: (1) SAEs; (2) nonserious adverse events (AEs); and (3) exposure to the study intervention under study during pregnancy or breastfeeding, and occupational exposure.

It should be noted that the CT SAE Report Form for reporting of SAE information is not the same as the AE page of the CRF. When the same data are collected, the forms must be completed in a consistent manner. AEs should be recorded using concise medical terminology and the same AE term should be used on both the CRF and the CT SAE Report Form for reporting of SAE information.

Safety Event	Recorded on the CRF	Reported on the CT SAE Report Form to Pfizer Safety Within 24 Hours of Awareness
SAE	All	All
Nonserious AE	All	None
Exposure to the study intervention under study during pregnancy or breastfeeding, and occupational exposure	All AEs/SAEs associated with exposure during pregnancy or breastfeeding  Occupational exposure is not recorded.	All (and EDP supplemental form for EDP) Note: Include all SAEs associated with exposure during pregnancy or breastfeeding. Include all AEs/SAEs associated with occupational exposure.

- When an AE/SAE occurs, it is the responsibility of the investigator to review all documentation (eg, hospital progress notes, laboratory reports, and diagnostic reports) related to the event.
- The investigator will then record all relevant AE/SAE information in the CRF.

- It is **not** acceptable for the investigator to send photocopies of the participant's medical records to Pfizer Safety in lieu of completion of the CT SAE Report Form/AE/SAE CRF page.
- There may be instances when copies of medical records for certain cases are requested by Pfizer Safety. In this case, all participant identifiers, with the exception of the participant number, will be redacted on the copies of the medical records before submission to Pfizer Safety.
- The investigator will attempt to establish a diagnosis of the event based on signs, symptoms, and/or other clinical information. Whenever possible, the diagnosis (not the individual signs/symptoms) will be documented as the AE/SAE.

#### **Assessment of Intensity**

The investigator will make an assessment of intensity for each AE and SAE reported during the study and assign it to 1 of the following categories:

- **Mild:** An event that is easily tolerated by the participant, causing minimal discomfort and not interfering with everyday activities.
- **Moderate:** An event that causes sufficient discomfort and interferes with normal everyday activities.
- **Severe:** An event that prevents normal everyday activities. An AE that is assessed as severe should not be confused with an SAE. Severe is a category utilized for rating the intensity of an event; and both AEs and SAEs can be assessed as severe.
- An event is defined as "serious" when it meets at least 1 of the predefined outcomes as described in the definition of an SAE, NOT when it is rated as severe.

#### **Assessment of Causality**

- The investigator is obligated to assess the relationship between study intervention and each occurrence of each AE/SAE.
- A "reasonable possibility" of a relationship conveys that there are facts, evidence, and/or arguments to suggest a causal relationship, rather than a relationship cannot be ruled out.
- The investigator will use clinical judgment to determine the relationship.

- Alternative causes, such as underlying disease(s), concomitant therapy, and other risk factors, as well as the temporal relationship of the event to study intervention administration, will be considered and investigated.
- The investigator will also consult the investigator's brochure and/or product information, for marketed products, in his/her assessment.
- For each AE/SAE, the investigator **must** document in the medical notes that he/she has reviewed the AE/SAE and has provided an assessment of causality.
- There may be situations in which an SAE has occurred and the investigator has minimal information to include in the initial report to the sponsor. However, **it is very important that the investigator always make an assessment of causality for every event before the initial transmission of the SAE data to the sponsor.**
- The investigator may change his/her opinion of causality in light of follow-up information and send an SAE follow-up report with the updated causality assessment.
- The causality assessment is one of the criteria used when determining regulatory reporting requirements.
- If the investigator does not know whether or not the study intervention caused the event, then the event will be handled as "related to study intervention" for reporting purposes, as defined by the sponsor. In addition, if the investigator determines that an SAE is associated with study procedures, the investigator must record this causal relationship in the source documents and CRF, and report such an assessment in the dedicated section of the CT SAE Report Form and in accordance with the SAE reporting requirements.

#### **Follow-up of AEs and SAEs**

- The investigator is obligated to perform or arrange for the conduct of supplemental measurements and/or evaluations as medically indicated or as requested by the sponsor to elucidate the nature and/or causality of the AE or SAE as fully as possible. This may include additional laboratory tests or investigations, histopathological examinations, or consultation with other healthcare providers.
- If a participant dies during participation in the study or during a recognized follow-up period, the investigator will provide Pfizer Safety with a copy of any postmortem findings including histopathology.
- New or updated information will be recorded in the originally completed CRF.

- The investigator will submit any updated SAE data to the sponsor within 24 hours of receipt of the information.

#### 10.3.4. Reporting of SAEs

SAE Reporting to Pfizer Safety via an Electronic Data Collection Tool

• The primary mechanism for reporting an SAE to Pfizer Safety will be the electronic data collection tool.

• If the electronic system is unavailable, then the site will use the paper SAE data collection tool (see next section) in order to report the event within 24 hours.

• The site will enter the SAE data into the electronic system as soon as the data become available.

• After the study is completed at a given site, the electronic data collection tool will be taken off-line to prevent the entry of new data or changes to existing data.

• If a site receives a report of a new SAE from a study participant or receives updated data on a previously reported SAE after the electronic data collection tool has been taken off-line, then the site can report this information on a paper SAE form (see next section) or to Pfizer Safety by telephone.

SAE Reporting to Pfizer Safety via CT SAE Report Form

• Facsimile transmission of the CT SAE Report Form is the preferred method to transmit this information to Pfizer Safety.

• In circumstances when the facsimile is not working, notification by telephone is acceptable with a copy of the CT SAE Report Form sent by overnight mail or courier service.

• Initial notification via telephone does not replace the need for the investigator to complete and sign the CT SAE Report Form pages within the designated reporting time frames.

## **10.4. Appendix 4: Contraceptive Guidance**

### **10.4.1. Female Participant Reproductive Inclusion Criteria**

A female participant is eligible to participate if she is not pregnant or breastfeeding, and at least 1 of the following conditions applies:

- Is not a WOCBP (see definitions below in Section 10.4.2).

OR

- Is a WOCBP and using an acceptable contraceptive method as described below during the intervention period (for a minimum of 28 days after the last dose of study intervention). The investigator should evaluate the effectiveness of the contraceptive method in relationship to the first dose of study intervention.

The investigator is responsible for review of medical history, menstrual history, and recent sexual activity to decrease the risk for inclusion of a woman with an early undetected pregnancy.

### **10.4.2. Woman of Childbearing Potential**

A woman is considered fertile following menarche and until becoming postmenopausal unless permanently sterile (see below).

If fertility is unclear (eg, amenorrhea in adolescents or athletes) and a menstrual cycle cannot be confirmed before the first dose of study intervention, additional evaluation should be considered.

Women in the following categories are not considered WOCBP:

1. Premenarchal.
2. Premenopausal female with 1 of the following:
  - Documented hysterectomy;
  - Documented bilateral salpingectomy;
  - Documented bilateral oophorectomy.

For individuals with permanent infertility due to an alternate medical cause other than the above, (eg, mullerian agenesis, androgen insensitivity), investigator discretion should be applied to determining study entry.

Note: Documentation for any of the above categories can come from the site personnel's review of the participant's medical records, medical examination, or medical history

interview. The method of documentation should be recorded in the participant's medical record for the study.

3. Postmenopausal female:

- A postmenopausal state is defined as no menses for 12 months without an alternative medical cause. In addition, a
  - high FSH level in the postmenopausal range must be used to confirm a postmenopausal state in women under 60 years of age and not using hormonal contraception or HRT.
  - Female on HRT and whose menopausal status is in doubt will be required to use one of the nonestrogen hormonal highly effective contraception methods if they wish to continue their HRT during the study. Otherwise, they must discontinue HRT to allow confirmation of postmenopausal status before study enrollment.

#### 10.4.3. Contraception Methods

Contraceptive use by men or women should be consistent with local availability/regulations regarding the use of contraceptive methods for those participating in clinical trials.

1. Implantable progestogen-only hormone contraception associated with inhibition of ovulation.
2. Intrauterine device.
3. Intrauterine hormone-releasing system.
4. Bilateral tubal occlusion.
5. Vasectomized partner:
  - Vasectomized partner is a highly effective contraceptive method provided that the partner is the sole sexual partner of the woman of childbearing potential and the absence of sperm has been confirmed. If not, an additional highly effective method of contraception should be used. The spermatogenesis cycle is approximately 90 days.
6. Combined (estrogen- and progestogen-containing) hormonal contraception associated with inhibition of ovulation:
  - Oral;
  - Intravaginal\*;

- Transdermal\*;
  - Injectable\*.
7. Progestogen-only hormone contraception associated with inhibition of ovulation\*:
- Oral;
  - Injectable.
8. Sexual abstinence:
- Sexual abstinence is considered a highly effective method only if defined as refraining from heterosexual intercourse during the entire period of risk associated with the study intervention. The reliability of sexual abstinence needs to be evaluated in relation to the duration of the study and the preferred and usual lifestyle of the participant.
9. Progestogen-only oral hormonal contraception where inhibition of ovulation is not the primary mode of action\*.
10. Male or female condom with or without spermicide.
11. Cervical cap\*, diaphragm, or sponge with spermicide\*.
12. A combination of male condom with either cervical cap\*, diaphragm, or sponge with spermicide\* (double-barrier methods).

\* Not approved or not certificated in Japan

## 10.5. Appendix 5: Liver Safety: Suggested Actions and Follow-up Assessments

### Potential Cases of Drug-Induced Liver Injury

Humans exposed to a drug who show no sign of liver injury (as determined by elevations in transaminases) are termed “tolerators,” while those who show transient liver injury, but adapt are termed “adaptors.” In some participants, transaminase elevations are a harbinger of a more serious potential outcome. These participants fail to adapt and therefore are “susceptible” to progressive and serious liver injury, commonly referred to as DILI. Participants who experience a transaminase elevation above  $3 \times \text{ULN}$  should be monitored more frequently to determine if they are an “adaptor” or are “susceptible.”

In the majority of DILI cases, elevations in AST and/or ALT precede TBili elevations ( $>2 \times \text{ULN}$ ) by several days or weeks. The increase in TBili typically occurs while AST/ALT is/are still elevated above  $3 \times \text{ULN}$  (ie, AST/ALT and TBili values will be elevated within the same laboratory sample). In rare instances, by the time TBili elevations are detected, AST/ALT values might have decreased. This occurrence is still regarded as a potential DILI. Therefore, abnormal elevations in either AST OR ALT in addition to TBili that meet the criteria outlined below are considered potential DILI (assessed per Hy’s law criteria) cases and should always be considered important medical events, even before all other possible causes of liver injury have been excluded.

The threshold of laboratory abnormalities for a potential DILI case depends on the participant’s individual baseline values and underlying conditions. Participants who present with the following laboratory abnormalities should be evaluated further as potential DILI (Hy’s law) cases to definitively determine the etiology of the abnormal laboratory values:

- Participants with AST/ALT and TBili baseline values within the normal range who subsequently present with AST OR ALT values  $>3 \times \text{ULN}$  AND a TBili value  $>2 \times \text{ULN}$  with no evidence of hemolysis and an alkaline phosphatase value  $<2 \times \text{ULN}$  or not available.
- For participants with baseline AST **OR** ALT **OR** TBili values above the ULN, the following threshold values are used in the definition mentioned above, as needed, depending on which values are above the ULN at baseline:
  - Preexisting AST or ALT baseline values above the normal range: AST or ALT values  $>2$  times the baseline values AND  $>3 \times \text{ULN}$ ; or  $>8 \times \text{ULN}$  (whichever is smaller).
  - Preexisting values of TBili above the normal range: TBili level increased from baseline value by an amount of at least  $1 \times \text{ULN}$  **or** if the value reaches  $>3 \times \text{ULN}$  (whichever is smaller).

Rises in AST/ALT and TBili separated by more than a few weeks should be assessed individually based on clinical judgment; any case where uncertainty remains as to whether it represents a potential Hy's law case should be reviewed with the sponsor.

The participant should return to the investigator site and be evaluated as soon as possible, preferably within 48 hours from awareness of the abnormal results. This evaluation should include laboratory tests, detailed history, and physical assessment.

In addition to repeating measurements of AST and ALT and TBili for suspected cases of Hy's law, additional laboratory tests should include albumin, CK, direct and indirect bilirubin, GGT, PT/INR, total bile acids, and alkaline phosphatase. Consideration should also be given to drawing a separate tube of clotted blood and an anticoagulated tube of blood for further testing, as needed, for further contemporaneous analyses at the time of the recognized initial abnormalities to determine etiology. A detailed history, including relevant information, such as review of ethanol, acetaminophen/paracetamol (either by itself or as a coformulated product in prescription or over-the-counter medications), recreational drug, supplement (herbal) use and consumption, family history, sexual history, travel history, history of contact with a jaundiced person, surgery, blood transfusion, history of liver or allergic disease, and potential occupational exposure to chemicals, should be collected. Further testing for acute hepatitis A, B, C, D, and E infection and liver imaging (eg, biliary tract) and collection of serum samples for acetaminophen/paracetamol drug and/or protein adduct levels may be warranted.

All cases demonstrated on repeat testing as meeting the laboratory criteria of AST/ALT and TBili elevation defined above should be considered potential DILI (Hy's law) cases if no other reason for the LFT abnormalities has yet been found. **Such potential DILI (Hy's law) cases are to be reported as SAEs, irrespective of availability of all the results of the investigations performed to determine etiology of the LFT abnormalities.**

A potential DILI (Hy's law) case becomes a confirmed case only after all results of reasonable investigations have been received and have excluded an alternative etiology.

## 10.6. Appendix 6: Abbreviations

The following is a list of abbreviations that may be used in the protocol.

Abbreviation	Term
%BSA	percent body surface area
AAP	American Academy of Pediatrics
AD	atopic dermatitis
ADSI	Atopic Dermatitis Severity Index
AE	adverse event
ALT	alanine aminotransferase
AST	aspartate aminotransferase
AUC	area under concentration-time curve
$\beta$ -hCG	beta-human chorionic gonadotropin
BID	bis in diem (twice a day)
BSA	body surface area
EASI	Eczema Area and Severity Index
CFR	Code of Federal Regulations
CIOMS	Council for International Organizations of Medical Sciences
CK	creatinine kinase
C max	maximum observed concentration
CONSORT	Consolidated Standards of Reporting Trials
CRF	case report form
CRO	contract research organization
CSR	clinical study report
CT	clinical trial
DILI	drug-induced liver injury
DMC	data monitoring committee
E-DMC	External Data Monitoring Committee
EC	ethics committee
EC 50	half maximal effective concentration
eCRF	electronic case report form
ECG	electrocardiogram
EDP	exposure during pregnancy
EMA	European Medicines Agency
EOS	end of study
EOT	end of treatment
ET	early termination
EU	European Union
EudraCT	European Clinical Trials Database
FSH	follicle-stimulating hormone
GCP	Good Clinical Practice
GGT	gamma glutamyl transferase
HIPAA	Health Insurance Portability and Accountability Act

Abbreviation	Term
HRQOL	health-related quality of life
HRT	hormone replacement therapy
IC 50	half maximal inhibitory concentration
ICD	informed consent document
ICH	International Council for Harmonisation
IFN	Interferon
IL	interleukin
IMP	investigational medicinal product
IND	investigational new drug
INR	international normalized ratio
IP manual	investigational product manual
IPAL	Investigational Product Accountability Log
IRB	institutional review board
IRT	interactive response technology
ISGA	Investigator's Static Global Assessment
JAK	Janus kinase
LFT	liver function test
MMP	matrix metalloproteinase
MUSE	maximal use, systemic exposure
N/A	not applicable
NIMP	noninvestigational medicinal product
NRS	Numeric Rating Scale
PDE	phosphodiesterase
PK	pharmacokinetic(s)
PRN	pro re nata
PT	prothrombin time
PUVA	psoralen plus ultraviolet A
QD	once a day
SAE	serious adverse event
SAP	statistical analysis plan
SOP	standard operating procedure
SRSD	single reference safety document
SoA	schedule of activities
SUSAR	suspected unexpected serious adverse reaction
t 1/2	half-life
TBili	total bilirubin
T max	time to reach maximum observed plasma concentration
TNF	tumor necrosis factor
TSS	Total Sign Scores
ULN	upper limit of normal
US	United States
UV	ultraviolet

Abbreviation	Term
UV-B	ultraviolet B
WOCBP	woman of childbearing potential

1. VERSION HISTORY

Table 1. Summary of Changes

Version/ Date	Associated Protocol Amendment	Rationale	Specific Changes
1 4 Aug 2020	Original 20 May 2020	N/A	N/A
2 7 Jan 2021	Original 20 May 2020	Study termination	Updated the following analyses due to the small sample size and the short exposure period. 6.4. Subset Analyses 6.5.3. Study Treatment Exposure 6.5.4. Concomitant Medications and Nondrug Treatments 6.6.1. Adverse Events

2. INTRODUCTION

This statistical analysis plan (SAP) provides the detailed methodology for summary and statistical analyses of the data collected in Study C3291027. This document may modify the plans outlined in the protocol; however, any major modifications of the primary endpoint definition or its analysis will also be reflected in a protocol amendment.

2.1. Study Objectives, Estimands and Endpoints

Objectives	Estimands	Endpoints
Primary:	Primary:	Primary:

 To study the safety of crisaborole ointment, 2% applied BID in Japanese pediatric and adult participants with mild to moderate AD. 	
 There is no defined estimand for this objective and these endpoints will be analyzed descriptively. 	
 The incidence of treatment emergent adverse events (TEAEs) and serious adverse events (SAEs).
Tertiary/Exploratory:	Tertiary/Exploratory:	Tertiary/Exploratory:

 To characterize the efficacy of long-term administration of crisaborole ointment, 2%. To characterize the patient/observer reported outcomes for pruritus of long-term administration of crisaborole ointment, 2%. 	
 There is no defined estimand for this objective and these endpoints will be analyzed descriptively. 	Efficacy* 
 % change from baseline in eczema area and severity index (EASI) over time. Achievement of EASI50 ($\geq 50\%$ improvement from baseline) over time. Achievement of EASI75 ($\geq 75\%$ improvement from baseline) over time. Change from baseline in Treatable % body surface area (BSA) over time. Achievement of success in investigator's static global assessment

Objectives	Estimands	Endpoints
		
(ISGA) [defined as an ISGA score of Clear (0) or Almost Clear (1) with at least a 2-grade improvement from baseline] over time.
 
 • Achievement of improvement in ISGA [defined as an ISGA score of Clear (0) or Almost Clear (1)] over time. • Achievement of success in Regional ISGA-face [defined as a Regional ISGA-face score of Clear (0) or Almost Clear (1) with at least a 2-grade improvement from baseline] over time. • Achievement of improvement in Regional ISGA-face [defined as a Regional ISGA-face score of Clear (0) or Almost Clear (1)] over time. • Incidence of the use of rescue medication (topical corticosteroids or topical calcineurin inhibitors). 
Patient/Observer Reported Outcomes
 
 • Change from baseline in Peak Pruritus NRS over time - for participants ≥ 12 years. • Changes from baseline in Patient Reported Itch Severity Scale over time - for participants ≥ 6 years and < 12 years. • Change from baseline in Observer Reported Itch Severity Scale over time - for participants < 6 years.

 • To assess the pharmacokinetic (PK) profile of crisaborole and its identified main oxidative metabolites (AN7602 and AN8323) following multiple topical doses of crisaborole ointment, 2% BID from C3291032 on Day 1. 	
 • There is no defined estimand for this objective and these endpoints will be analyzed descriptively. 	
 • Plasma concentrations of crisaborole and its identified main oxidative metabolites (AN7602 and AN8323) on Day 1.

* Baseline refers to the baseline data of Study C3291032 or Study C3291031.

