2.2. Study Design

This study is a Phase 3, multicenter, open-label, long-term safety extension study of Studies C3291032 and C3291031 in Japanese pediatric and adult participants with mild to moderate AD to support the registration of crisaborole in Japan. After completion of the study intervention period in Study C3291032 or Study C3291031 and confirmed Study C3291027 eligibility, participants will be offered participation in the study from investigator sites in Japan. The sample size of this study is approximately 150 participants but will be determined by the number of participants who complete Study C3291032 treatment period or

Study C3291031 treatment period and meet eligibility criteria of this study. Scheduled study visits will occur every 4 weeks (1 cycle) with On-Treatment or Off-Treatment cycles to be decided by the investigator based on the ISGA score. PK blood sampling will be conducted at the selected study sites for the participants aged between 2 years old and 11 years old at the time of signing the ICD in Study C3291032.

When the investigator assessment of ISGA is Almost Clear (1) or greater, an On-Treatment Cycle will be initiated. When the investigator assessment of ISGA is Clear (0), crisaborole ointment, 2% treatment will not be initiated and the participant will enter an Off-Treatment Cycle. Based on the ISGA score throughout the study, a participant may be administered a variable number of cycles of crisaborole ointment, 2% treatment (On-Treatment Cycle) during their up to 52 weeks of study participation.

On Week 56 (End of Study), a follow-up telephone call will be made by site staff to assess for AEs that may have occurred since the last visit.

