5.2. General Methods

In general, for descriptive analyses, number and percentage will be presented for binary variables. Number and percentage will be presented for categorical variables. Number, mean, median, standard deviation, minimum and maximum will be presented for continuous variables.

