5.3. Methods to Manage Missing Data

In general, for analyses using descriptive statistics, missing values will not be imputed. In addition, for safety endpoints, missing values will not be imputed. Other methods for handling missing values are discussed below.

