- Analysis Methodology: Descriptive statistics (see [Section 5.2](#)) and 95% two-sided confidence intervals for incidence of the use of rescue medication (topical corticosteroids or topical calcineurin inhibitors).

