6.5.4. Concomitant Medications and Nondrug Treatments

Concomitant drug and non-drug treatment will be summarized according to CaPs. Number of days when rescue medication is taken will be descriptively summarized for All-Treatment Period, respectively.

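### Rescue-medication incidence is planned as a crude percentage with no time horizon, so after early termination it cannot be interpreted without follow-up time

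*SAP*

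**What the plan says.** SAP 2.1 and 3.3.1.1 name the endpoint: "Incidence of the use of rescue medication (topical corticosteroids or topical calcineurin inhibitors". It is the only efficacy endpoint in that list that is not specified over time. SAP 6.3.1.9 assigns it to the full analysis set, with descriptive statistics and "95% two-sided confidence intervals for incidence of the use of rescue medication". SAP 5.2 defines the descriptive part: "number and percentage will be presented for binary variables". On incomplete follow-up, SAP 5.3 says only that "for analyses using descriptive statistics, missing values will not be imputed".

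Participants may receive a variable number of treatment cycles "during their up to 52 weeks of study participation" (SAP 2.2). Under the schedule of activities (Protocol 1.3), each person's Day 1 is the end-of-treatment visit of the parent study, so entry is staggered.

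SAP version 2 (7 Jan 2021) gives study termination as its rationale and states: "Updated the following analyses due to the small sample size and the short exposure period". It lists 6.4, 6.5.3, 6.5.4 and 6.6.1 as changed; 6.3.1.9 is not on the list.

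Two other sections bear on the point. SAP 6.5.3 summarises treatment duration, number of applications, and on- and off-treatment cycle counts. SAP 6.5.4 adds: "Number of days when rescue medication is taken will be descriptively summarized for All-Treatment Period".

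**The concern.** The other efficacy endpoints are read at each visit, and SAP Appendix 1 assigns them to visit windows, so each figure carries its own time point. Rescue use is different. It is an event that either has or has not happened by the time observation ends, and the chance that it has happened grows with observation. In a crude percentage, a participant followed for 4 weeks without rescue counts the same as one followed for 28 weeks without rescue.

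Had everyone completed 52 weeks, the percentage would at least have had an implied horizon. Termination removes it. What is at stake is interpretation. The stated objective is to characterise efficacy under long-term administration, in a study meant to support registration in Japan. A low percentage could be taken as sustained control when part of the explanation may be short observation. The confidence interval does not help, because it describes sampling error around a quantity whose horizon is undefined.

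**Working it through.** The documents give no rescue rate, precision target or expected percentage, so there is no stated figure to reproduce. The check has three parts.

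**1. How long could follow-up have been?**
- The protocol is dated 20 May 2020 and describes both parent studies as still planned (Protocol 2.1). SAP version 2 is dated 7 Jan 2021. The interval is 232 days, and 232/7 = 33.1 weeks.
- Entrants from C3291032 join at its Day 29: 232 − 28 = 204 days, at most 29.1 weeks.
- Entrants from C3291031 join at its Week 24: 232 − 168 = 64 days, at most 9.1 weeks.

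These bounds assume that no parent enrolment preceded the protocol date and that follow-up ended by the SAP version 2 date. On those assumptions nobody reached Week 52.

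**2. How far does the crude percentage move with follow-up?** Assume a constant hazard λ = −ln(1 − p52)/52 per week, where p52 is an assumed 52-week risk of first rescue use. If everyone is followed for T weeks, the expected crude percentage is 1 − exp(−λT). For p52 = 20%, λ = 0.2231/52 = 0.00429.

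| Assumed 52-week risk | T = 4 | T = 12 | T = 29 | T = 52 |
|---|---|---|---|---|
| 10% | 0.8% | 2.4% | 5.7% | 10.0% |
| 20% | 1.7% | 5.0% | 11.7% | 20.0% |
| 40% | 3.9% | 11.1% | 24.8% | 40.0% |

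If follow-up is instead spread uniformly over 0 to 29 weeks, the crude figure is 1 − [1 − exp(−29λ)]/(29λ), which gives 2.9%, 6.0% and 13.0% for the three rows.

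The reverse reading shows the ambiguity. A crude 10% corresponds to a 52-week risk of 1 − 0.9^(52/T): 49.6% if all had 8 weeks, 20.4% if 24 weeks, 10.0% if 52 weeks. Under the same model, the rate per person-time does not depend on T. For the 20% row it is 0.00429 × 52.18 × 100 = 22.4 first uses per 100 person-years.

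**3. Do other planned tables supply the missing time?**
- Treatment duration (SAP 6.5.3) is the interval between first and last dose. That is not time at risk of rescue. It is undefined for anyone who starts off treatment and is never dosed, yet SAP 4 includes participants whose first cycle is off treatment, and Protocol 6.1.1 allows rescue in such cycles.
- Cycle counts (SAP 6.5.3) approximate observation time for the group, since a cycle is 4 weeks, but they are not linked to who used rescue.
- Rescue days (SAP 6.5.4) have no follow-up denominator. Continuous rescue for more than 28 days also ends participation (Protocol 6.5.3), which shortens follow-up for those users.

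**The case against.** The strongest defence is that this is one of nine exploratory efficacy endpoints in a single-arm study with no estimand and no hypothesis test. A count over the number treated is a correct description of what was observed. The protocol names exposure-adjusted rates only for the primary safety endpoint (Protocol 9.4.2), so the crude percentage departs from nothing. The SAP itself declares the short exposure, and cycle counts, treatment duration and disposition will be tabulated. All of this stands. It limits the weight of the point, but those tables still leave rescue use unconnected to time at risk.

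Three stronger readings are tempting, and the documents do not support them.
- *That the percentage mainly reflects observation time.* No rescue rate, number enrolled, follow-up distribution or termination date is given. Follow-up of 4 to 29 weeks spans a factor of 29/4 = 7.3. The hazard spans a factor of 4.8 if the 52-week risk lies between 10% and 40%, and 17.9 if between 5% and 60%. Either could dominate.
- *That it understates the need for rescue.* It is lower only relative to a longer horizon, and 6.3.1.9 does not claim to estimate one.
- *That follow-up alone changes the figure four- to six-fold.* With follow-up uniform over a to b weeks, the expected crude figure is 1 − [exp(−λa) − exp(−λb)]/[λ(b − a)]. For 52-week risks of 20%, 40% and 60%, this gives 3.4%, 7.5% and 13.1% over 4 to 12 weeks. The ratios to the 52-week risk are 5.9, 5.3 and 4.6. Over 4 to 29 weeks it gives 6.8%, 14.7% and 24.6%, with ratios 2.9, 2.7 and 2.4. The larger factor needs the shorter window, and both compare with a Week 52 that, on the date bound, nobody reached.

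**Conclusion.** The point holds as a minor one. Rescue use accumulates with observation, and its planned summary is a percentage with no horizon, person-time or censoring rule. Staggered entry and early termination make follow-up short and unequal. The percentage and its interval are therefore not interpretable, and cannot serve as a long-term or 52-week incidence, without the follow-up time beside them.

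The illustrated size, 1.7% to 11.7% for the same assumed 20% risk as follow-up goes from 4 to 29 weeks, rests on a constant hazard and an assumed risk. The 29-week limit rests on the document dates. The actual effect cannot be computed from the documents. That the percentage depends on follow-up does not rest on the particular hazard chosen.

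**What to change.** In SAP 6.3.1.9:
- Keep the number and percentage of the full analysis set.
- Show total participant-weeks of follow-up beside it, from C3291027 Day 1 to last study contact.
- Add the rate of first rescue use per person-time with a 95% confidence interval. Time runs from Day 1 to first rescue use, or to last study contact for those without it.
- Optionally, add a Kaplan-Meier cumulative incidence, only at weeks with adequate numbers at risk. It should not replace the count as the main summary in a small terminated sample. On the date bound, entrants from C3291031 could not have reached Week 12.

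In SAP 6.5.4, also express each participant's rescue days as a percentage of that participant's follow-up days.

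No new data are needed: start and end dates of concomitant treatments are already recorded (Protocol 6.5), as are rescue prescriptions (Protocol 6.5.3). The cost is a change of SAP wording and one extra table. The downside is that the added intervals will be wide in a small sample.
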